4.2 Bupropion

4.2.1 Rationale for Studying Bupropion

Bupropion is an attractive candidate medication for the treatment of methamphetamine dependence for several reasons:

- 1. Bupropion is an antidepressant with stimulant properties⁹⁶ that is effective for the treatment of nicotine dependence.⁹⁷
- 2. In a clinical trial of bupropion for cocaine dependence⁹⁸ an exploratory analysis suggested that patients with greater levels of depression may have benefited the most. The association with improvement in patients with depression is promising for methamphetamine dependence as clinically, acute abstinence from methamphetamine in chronic users is associated with depression and impaired concentration.⁹⁹
- 3. Bupropion's pharmacologic activities are thought to operate through a dopaminergic mechanism which when combined with its ability to alleviate the dysphoria seen in early abstinence may reduce craving, thus helping to prevent relapse.
- 4. Bupropion was found to be safe in clinical laboratory studies assessing its effects when administered concurrently with intravenous methamphetamine.^{100,101}
- 5. A Phase 2 efficacy study showed that bupropion significantly decreased methamphetamine use in methamphetamine dependent subjects who were using methamphetamine 18 days or less in the 30-day period prior to the start of screening (described below).

Bupropion is an antidepressant of aminoketone class that is chemically unrelated to tricyclic, tetracyclic, selective serotonin reuptake inhibitors (SSRIs), or other known antidepressant agents. The mechanism of its antidepressant action may be related to its mild dopaminergic activity. Bupropion is considered to be a dopaminergic antidepressant based on its ability to inhibit the uptake of dopamine more selectively than it inhibits uptake of norepinephrine or serotonin. Bupropion has a favorable side effect profile: it causes fewer anticholinergic, cardiovascular, sedative or adverse sexual effects than tricyclics and does not cause weight gain.¹⁰²

Bupropion is a relatively weak inhibitor of the neuronal reuptake of dopamine and thus has a low abuse liability.¹⁰³ Its potency to block dopamine reuptake in animals manifests at doses higher than those necessary for its antidepressant effect. It is possible however that the mild dopaminergic activity that bupropion does possess is sufficient to exert anti-craving effect and to treat the signs of withdrawal.

Bupropion has been proved to be effective for treatment of nicotine dependence^{104,105} and is FDA-approved and marketed as Zyban, a non-nicotine aid to smoking cessation. Bupropion has been investigated for treatment of cocaine abuse. In a pilot study, Margolin *et al.*¹⁰⁶ found that bupropion 300 mg/day, administered to five cocaine-dependent methadone-maintenance patients substantially reduced cocaine use in four of the five, was well tolerated and reduced self-reported craving for cocaine. A multicenter placebo-controlled double-blind clinical trial of bupropion for cocaine dependence in methadone-maintenance patients indicates efficacy of bupropion for the subgroup of patients with depression at study entry.⁹⁸

The results of animal studies designed to test the ability of bupropion to block effects of methamphetamine support clinical use for the treatment of methamphetamine dependence.¹⁰⁷

[figure not shown]
Thus, bupropion provides complete protection against methamphetamine-induced decrease in dopamine uptake in striatum in *in vitro* model of methamphetamine-induced dopamine nerve terminal toxicity. It is logical to postulate that combination of bupropion's dopaminergic activity and antidepressant properties may guarantee its efficacy in clinical trials for treatment and relief of the signs and symptoms of methamphetamine withdrawal and for prevention of the relapse.

[figure not shown]
4.2.2 Molecular Mechanism for Bupropion's Potential Efficacy for Methamphetamine Dependence

[figure not shown]
Bupropion may be effective for methamphetamine dependence due to its ability to counteract methamphetamine-induced alterations in molecules regulating synaptic dopamine disposition. Recent studies have shown that psychostimulants produce their effects on dopaminergic neurotransmission via disruption of key molecules responsible for regulating the disposition of dopamine within the synapse and neuronal cytoplasm. Normally, dopamine released from synaptic vesicles in response to an action potential is cleared from the synapse by re-uptake into the presynaptic neuron via the dopamine transporter DAT and/or by metabolism by the enzyme COMT. After re-uptake into the cytoplasm, dopamine is sequestered into synaptic vesicles by transport via vesicular monoamine transporter-2 (VMAT-2), in order to prevent the generation of toxic reactive oxygenation species (ROS) that are produced by accumulation of dopamine within the cytoplasm. Further protection against ROS-induced toxicity is provided by the glutathione S-

transferase family of enzymes, which catalyze conjugation of reduced glutathione with ROS that are generated.

Psychostimulants cause an acute increase in synaptic dopamine concentrations and can be divided into two groups, which Hanson and colleagues have termed "releasers" and "uptake blockers," based on their mechanism of action.¹⁰⁸ Releasers (**Figure 1**), such as methamphetamine, increase synaptic dopamine levels by producing increased release of dopamine from presynaptic neurons. Methamphetamine is highly lipophilic and thereby diffuses into synaptic vesicles where it disrupts the vesicular proton gradient necessary for functioning of VMAT-2, resulting in impaired sequestering of cytosolic dopamine into vesicles. ^{109,110} As a result, dopamine accumulates in the cytoplasm leading to increased release of dopamine into the synapse by reverse transport via DAT.^{110,111} In addition to disrupting VMAT-2 function, MA also causes trafficking of VMAT-2 containing vesicles out of the neuronal cytoplasm, thereby reducing the pool of synaptic vesicles available to sequester dopamine and further increasing cytoplasmic dopamine accumulation.¹¹² While the mechanism by which releasers cause this vesicular trafficking is not clear, activation of D2 dopamine receptors (DRD2) is required, ¹¹³ suggesting that methamphetamine-induced increases in synaptic dopamine may activate presynaptic DRD2 receptors which then trigger vesicular trafficking.

In addition to these molecular changes, chronic methamphetamine use also produces significant damage to dopaminergic neurons and deficits in dopaminergic function. Preclinical studies have shown that high-dose methamphetamine exposure produces neurotoxic changes among dopaminergic cells in the striatum as well as deficits in striatal tyrosine hydroxylase activity, dopamine concentrations, and DAT levels. ¹¹⁴⁻¹¹⁸ Clinical imaging studies have also shown significant deficits in dopaminergic function among chronic methamphetamine users, including reductions in DAT density ¹¹ and dopamine receptor occupancy, ^{4,119} which are thought to contribute to the clinical symptoms that accompany methamphetamine dependence and withdrawal. This methamphetamine-induced neurotoxicity and the resulting deficits in dopamine gic function result in part from harmful intracellular ROS that are produced when dopamine accumulates in the cytoplasm.^{120,121} As a result, medications that counteract the methamphetamine-induced disruptions in VMAT-2 function, have potential as treatments for methamphetamine dependence due to their ability to minimize damage due to disruptions in dopaminergic function produced by chronic methamphetamine use.

Reuptake blockers (Figure 1), such as the antidepressant bupropion, bind to DAT, thereby blocking transport of dopamine from the synapse into the cytoplasm, and increasing synaptic dopamine levels. ^{122,123} In addition, reuptake blockers also increase VMAT-2 function and trigger trafficking of VMAT-2 containing vesicles into the cytoplasm of presynaptic neurons again via an unknown DRD2 mediated mechanism, thereby increasing vesicular dopamine uptake.^{124,125} As a result, cytoplasmic accumulation of dopamine and subsequent ROS formation does not occur with reuptake blockers, and furthermore as a result of their effect on VMAT-2, reuptake blockers may be effective in reversing the disruptions in VMAT-2 functioning and subsequent neurotoxicity caused by releasers including methamphetamine. In fact, preclinical studies have shown that post-treatment with the reuptake blockers methylphenidate and bupropion after treatment with methamphetamine did reverse the methamphetamine-induced reductions in VMAT-2 activity, but *bupropion did not* prevent the long-term deficits in dopaminergic function produced by repeated high-dose methamphetamine administration.^{125,126} While the reasons for this have not been established experimentally, frequent high-dose methamphetamine use may simply overcome bupropion's ability to counteract methamphetamine-induced alterations in dopamine disposition.

In summary, methamphetamine has profound effects on molecules that regulate synaptic dopamine disposition and acute methamphetamine administration results in release of dopamine which is thought to contribute to the subjective effects of methamphetamine. Frequent high-dose methamphetamine use results in accumulation of toxic ROS that contribute to the deficits in dopaminergic function that are seen clinically in chronic methamphetamine users. Dopamine re-uptake inhibitors, such as bupropion, may be effective treatments for methamphetamine dependence due to their ability increase synaptic dopamine levels, thereby ameliorating methamphetamine-induced deficits in dopaminergic function, and to counteract methamphetamine-induced alterations in dopamine disposition and subsequent ROS formation via enhanced vesicular dopamine uptake. Yet the failure of bupropion to prevent long-term dopaminergic deficits after repeated high-dose methamphetamine in preclinical studies suggests that bupropion's clinical utility for methamphetamine dependence may be limited to low frequency methamphetamine users.

4.2.3 Bupropion Pharmacology

Pharmacokinetics. Tablets of bupropion hydrochloride come in immediate- and SR formulations. The bupropion SR, 150 mg, twice daily formulation will be used for this study. Bupropion SR has been shown to be bioequivalent to 100 mg three times daily of the immediate release formulation with regards to rate and extent of absorption and parent drug and metabolites in clinical trials for depression. Better compliance is expected with twice daily dosing as opposed to thrice daily dosing making bupropion SR an obvious choice for study.

The half-life of bupropion is approximately 21 hours after chronic dosing. Peak plasma concentrations of bupropion are achieved within 3 hours following oral administration. The mean peak concentration (C_{max}) values were 91 and 143 ng/mL from 2 single-dose (150-mg) studies. At steady state, the mean C_{max} following a 150-mg dose every 12 hours is 136 ng/mL. In a single-dose study, food increased the C_{max} of bupropion by 11% and the extent of absorption as defined by area under the plasma concentration-time curve (AUC) by 17%. The mean time to peak concentration (T_{max}) was prolonged by 1 hour. This effect was of no clinical significance. Steady state plasma concentrations of bupropion are reached within 8 days. Four basic metabolites have been identified. These metabolites are pharmacologically active, but their potency and toxicity relative to bupropion have not been totally characterized. They may be of clinical importance because the plasma concentration of metabolites is higher than those of bupropion.

Bupropion is a racemic mixture. The pharmacologic activity and pharmacokinetics of the individual enantiomers have not been studied. Bupropion follows biphasic pharmacokinetics best described by a 2-compartment model. The terminal phase has a mean half-life (\pm % CV) of about 21 hours (\pm 20%), while the distribution phase has a mean 57 half-life of 3 to 4 hours.

In vitro tests show that bupropion is 84% bound to human plasma proteins at concentrations up to 200 μ g/mL. The extent of protein binding of the hydroxybupropion metabolite is similar to that for bupropion, whereas the extent of protein binding of the threohydrobupropion metabolite is about half that seen with bupropion. The volume of distribution (V_{ss}/F) estimated from a single 150-mg dose given to 17 subjects is 1,950 L (20% CV).

Metabolism. Bupropion is extensively metabolized in humans. Three metabolites have been shown to be active: hydroxybupropion, which is formed via hydroxylation of the *tert*-butyl group of bupropion, and the amino-alcohol isomers threohydrobupropion and erythrohydrobupropion, which are formed via reduction of the carbonyl group. *In vitro* findings suggest that CYP2B6 is the principal isoenzyme involved in the formation of hydroxybupropion. While cytochrome P450 isoenzymes are not involved in the formation of threohydrobupropion. Oxidation of the bupropion side chain results in the formation of a glycine conjugate of meta-chlorobenzoic acid, which is then excreted as the major urinary metabolite. The potency and toxicity of the metabolites relative to bupropion have not been fully characterized. However, it has been demonstrated in an antidepressant screening test in mice that hydroxybupropion are 5-fold less potent than bupropion. This may be of clinical importance because the plasma concentrations of the metabolites are as high or higher than those of bupropion.

Because bupropion is extensively metabolized, there is the potential for drug-drug interactions, particularly with those agents that are metabolized by the CYP2B6 isoenzyme. Although bupropion is not metabolized by CYP2D6, there is the potential for drug-drug interactions when bupropion is co-administered with drugs metabolized by this isoenzyme. Following a single dose in humans, peak plasma concentrations of hydroxybupropion occur approximately 6 hours after administration of bupropion SR. Peak plasma concentrations of hydroxybupropion are approximately 10 times the peak level of the parent drug at steady state. The elimination half-life of hydroxybupropion is approximately 20 (\pm 5) hours, and its AUC at steady state is about 17 times that of bupropion. The times to peak concentrations for the erythrohydrobupropion and threohydrobupropion metabolites are similar to that of the hydroxybupropion metabolite; however, their elimination half-lives are longer, 33 (\pm 10) and 37 (\pm 13) hours, respectively, and steady-state AUCs are 1.5 and 7 times that of bupropion, respectively. Bupropion and its metabolites exhibit linear kinetics following chronic administration of 300 to 450 mg/day.

4.2.4 Previous Human Experience with Bupropion in Methamphetamine Dependence

Phase 1 and Phase 2 clinical trials assessing the safety and efficacy of bupropion for methamphetamine dependence have been conducted with positive outcomes. In a Phase 1 clinical laboratory study, 26 subjects with a diagnosis of methamphetamine dependence or abuse by DSM-IV criteria were randomized in a double-blind in-patient study to receive either twice daily bupropion SR (150 mg BID) or placebo control and infusions of saline or 15 mg and 30 mg of methamphetamine. Of the 26 subjects who were enrolled, 20 completed the entire study with 10 subjects in each of the bupropion and placebo control groups. Bupropion treatment was associated with reduced ratings of "any drug effect" (p=0.02), and "high" (p=0.02) that were assessed with visual analog scales following methamphetamine administration. Bupropion also significantly reduced cue-induced craving [General Craving Scale total score (p=0.002); Behavioral Intention subscale (p=0.001)].¹⁰⁰ Bupropion treatment was well tolerated, with the bupropion- and placebo-treated groups reporting similar rates of AEs. Methamphetamine administration was associated with the expected stimulant cardiovascular effects, and these were not accentuated by bupropion treatment. Instead, there was a trend for bupropion to reduce methamphetamine-associated increases in blood pressure and a statistically significant reduction in methamphetamine-associated increases in heart rate. Pharmacokinetic analysis revealed that bupropion treatment reduced the plasma clearance of methamphetamine and also reduced the appearance of amphetamine in the plasma. Methamphetamine administration did not alter the peak and trough plasma concentrations of bupropion or its metabolites.¹⁰¹

NIDA conducted a Phase 2 study evaluating bupropion for methamphetamine dependence (Protocol Number CTO-0008). This study was of similar design to the present study, except that subjects in the first study were selected from a group of methamphetamine users that was not restricted to low use prior to the start of the study (i.e., low use being defined in the current study population as ≤ 18 days of methamphetamine use in the 30 day period before the start of screening). The CTO-0008 study was a double-blind, placebo-controlled, randomized, two arm parallel-group study comparing 150 mg of bupropion to placebo administered twice daily to methamphetamine dependent outpatients. One hundred one (151) subjects were in the ITT population, of which 121 subjects were considered evaluable. The major conclusions regarding the efficacy of bupropion in this study were as follows:

- 1. Analysis of the primary outcome measure (weekly proportion of subjects with all urine specimens free of methamphetamine) showed a trend toward statistical significance favoring bupropion over placebo for the entire population (GEE, p=0.09).
- 2. Bupropion showed a statistically significant effect for weekly methamphetamine-free week in subjects who used methamphetamine 18-days or less in the 30 days prior to the start of screening (GEE, p<0.04).
- 3. More subjects in the bupropion group than the placebo group reduced their proportion of methamphetamine use days to 50% or less of their baseline rate based on self report only (Chi-square test, p=0.02).
- 4. Bupropion showed a statistically significant effect for weekly methamphetamine-free week in males (GEE, p=0.04).
- 5. Bupropion showed a trend toward significance favoring bupropion for methamphetamine-free week in non-depressed subjects (GEE, p=0.08).
- 6. Bupropion showed a statistically significant effect for weekly methamphetamine-free week in subjects without ADD (GEE, p=0.02).

4.2.5 Safety of Bupropion

Contraindicated Conditions. Bupropion (ZYBAN Package Insert March 2007) is contraindicated in subjects:

- 1. With a seizure disorder.
- 2. Who are concurrently using a bupropion containing medication because the incidence of seizure is dose dependent.
- 3. Who have a current or prior diagnosis of bulimia or anorexia nervosa because of a higher incidence of seizures noted in patients treated for bulimia with the immediate-release formulation of bupropion.
- 4. Who are abruptly discontinuing alcohol or sedatives (including benzodiazepines).
- 5. Who are concurrently taking a monoamine oxidase (MAO) inhibitor (at least 14 days should elapse between discontinuation of an MAO inhibitor and initiation of bupropion administration).
- 6. Who have had an allergic response to bupropion.
- 7. Who have major depressive disorder (patients may experience worsening of their depression and/or the emergence of suicidal ideation and behavior (suicidality) or unusual changes in behavior, whether or not they are taking antidepressant medications, and this risk may persist until significant remission occurs). There has been a long-standing concern that antidepressants may have a role in inducing worsening of depression and the emergence of suicidality in certain patients.

AEs Associated With the Discontinuation of Treatment. AEs leading to discontinuation of treatment with bupropion SR included nervous system disturbances 655 (3.4%), primarily tremors, and skin disorders (2.4%), primarily rashes.

Incidence of Commonly Observed Adverse Events. The most commonly observed AEs (those that consistently occurred at a rate of 5 percentage points greater than that for placebo across clinical studies) consistently associated with the use of bupropion SR were dry mouth and insomnia.

Risk of Seizure. Predisposing factors that may increase the risk of seizure with bupropion use include history of head trauma or prior seizure, central nervous system (CNS) tumor, the presence of severe hepatic cirrhosis, and concomitant medications that lower seizure threshold. Circumstances associated with an increased seizure risk include, among others, excessive use of alcohol or sedatives (including benzodiazepines); addiction to opiates, cocaine, or stimulants; use of over-the-counter stimulants and anorectics; and diabetes treated with oral hypoglycemics or insulin. Concomitant medications such as antipsychotics, antidepressants, theophylline, and systemic steroids are known to lower seizure threshold. The risk of seizure may be minimized if

the total daily dose of bupropion SR dose not exceed 300 mg, which is the dose planned in this study.

In addition, bupropion SR should be administered with extreme caution to subjects with a history of seizure, cranial trauma, or other predisposition(s) toward seizure, or patients treated with other agents (e.g., antipsychotics, antidepressants, theophylline, systemic steroids, etc.) that lower seizure threshold. These subjects will be excluded from participation in the study; moreover, these medications are prohibited during the intervention phase of the study.

Allergic Reactions. Anaphylactoid/anaphylactic reactions characterized by symptoms such as pruritus, urticaria, angioedema, and dyspnea requiring medical treatment have been reported at a rate of about 1 to 3 per thousand in clinical trials of bupropion SR. In addition, there have been rare spontaneous postmarketing reports of erythema multiforme, Stevens-Johnson syndrome, and anaphylactic shock associated with bupropion. Subjects will be advised to stop taking investigational products and consult a doctor if experiencing allergic or anaphylactoid/ anaphylactic reactions (e.g., skin rash, pruritus, hives, chest pain, edema, and shortness of breath) during treatment. Arthralgia, myalgia, and fever with rash and other symptoms suggestive of delayed hypersensitivity have been reported in association with bupropion. These symptoms may resemble serum sickness.

Insomnia. In the dose-response smoking cessation trial, 29% of patients treated with 150 mg/day of bupropion SR and 35% of patients treated with 300 mg/day of bupropion SR experienced insomnia, compared to 21% of placebo-treated patients. Symptoms were sufficiently severe to require discontinuation of treatment in 0.6% of patients treated with bupropion SR and none of the patients treated with placebo.

Neuropsychiatric Side Effects. In clinical trials with bupropion SR conducted in nondepressed smokers, the incidence of neuropsychiatric side effects was generally comparable to placebo. Depressed patients treated with bupropion in depression trials have been reported to show a variety of neuropsychiatric signs and symptoms including delusions, hallucinations, psychosis, concentration disturbance, paranoia, and confusion. In some cases, these symptoms abated upon dose reduction and/or withdrawal of treatment.

Antidepressants can precipitate manic episodes in bipolar disorder patients during the depressed phase of their illness and may activate latent psychosis in other susceptible individuals. The SR formulation of bupropion is expected to pose similar risks.

Cardiovascular Conditions. In clinical practice, hypertension, in some cases severe, requiring acute treatment, has been reported in patients receiving bupropion SR alone and in combination with nicotine replacement therapy. These events have been observed in both patients with and without evidence of preexisting hypertension. Data from a comparative study of ZYBAN, nicotine transdermal system (NTS), the combination of bupropion SR plus NTS, and placebo as an aid to smoking cessation suggest a higher incidence of treatment-emergent hypertension in patients treated with the combination of bupropion SR and NTS. In this study, 6.1% of patients treated with the combination of bupropion SR and NTS had treatment-emergent hypertension compared to 2.5%, 1.6%, and 3.1% of patients treated with bupropion SR, NTS, and placebo,

respectively. The majority of these patients had evidence of preexisting hypertension. Three patients (1.2%) treated with the combination of bupropion SR and NTS and 1 patient (0.4%) treated with NTS had study medication discontinued due to hypertension compared to none of the patients treated with bupropion SR or placebo.

Subjects will be asked to inform a study physician, if they decide to use any smoking cessation products such as nicotine gum, nicotine patch, nicotine nasal spray or nicotine inhaler while on study. If any agents are used, blood pressure should be monitored closely as bupropion may increase blood pressure when used with these smoking cessation agents.

Drug Interactions. In vitro studies indicate that bupropion is primarily metabolized to hydroxybupropion by the CYP 2B6 isoenzyme. Therefore, the potential exists for a drug interaction between bupropion SR and drugs that are substrates or inhibitors of the CYP 2B6 isoenzyme (e.g., orphenadrine, thiotepa, and cyclophosphamide). In addition, *in vitro* studies suggest that paroxetine, sertraline, norfluoxetine, and fluvoxamine as well as nelfinavir, ritonavir, and efavirenz inhibit the hydroxylation of bupropion. No clinical studies have been

performed to evaluate this finding. The threohydrobupropion metabolite of bupropion does not appear to be produced by the CYP isoenzymes.

Because bupropion is extensively metabolized, the coadministration of other drugs may affect its clinical activity. In particular, certain drugs may induce the metabolism of bupropion (e.g., carbamazepine, phenobarbital, phenytoin), while other drugs may inhibit the metabolism of bupropion (e.g., cimetidine).

Reproductive Toxicology. Bupropion is a pregnancy Category C drug.

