- 9. Have diabetes with unstable control of blood glucose and have any incidence of hypoglycemia in the past year before screening.
- 10. Be mandated by the court to obtain treatment for methamphetamine-dependence where such mandate required the results of urine toxicology tests to be reported to the court.
- 11. In the opinion of the investigator, be expected to fail to complete the study protocol due to probable incarceration or relocation from the clinic area.
- 12. Be undergoing HIV treatment with antiviral and/or non-antiviral therapy since these drugs may increase the bupropion levels. The following list of HIV treatment/medications may be

used: Norvir, Reyataz, Truvada, Videx, Viread, Androgel and Trizovir. Note: Any HIV medication not on this list should be approved by the medical monitor.

- 13. Have known or suspected hypersensitivity to bupropion.
- 14. Be using bupropion or any medication that could interact adversely with bupropion, within the following times of beginning of administration of bupropion based on the longest time interval of A, B, and C, below or as otherwise specified:
 - A) Five half lives of other medication or active metabolite(s), whichever is longer;
 - B) Two weeks; or
 - C) Interval recommended by other medication's product labeling.

Medications that fall into this category include:

- a. Bupropion (Wellbutrin[®], Zyban[®]) used during the past 30 days
- b. All antidepressants
- c. Neuroleptics
- d. Systemic corticosteroids
- e. Xanthines, i.e., theophilline, theophilline sodium glycinate and aminophylline
- f. Antiretrovirals including nelfinavir, and efavirenz
- g. Tramadol (Ultram, Ultram Extended Release)
- 15. Have participated in any experimental study within 8 weeks (the nature of excluded studies may be discussed with NIDA investigators).
- 16. Be pregnant or breast feeding.
- 17. Have clinically significant laboratory values (outside of normal limits), in the judgment of the investigator.
- 18. Have liver function tests greater than 3 times the upper limit of normal.
- 19. Have active tuberculosis (positive tuberculin test and confirmatory diagnostic chest x-ray).

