12.13 Concomitant Medications

Any medications (including prescription, over-the-counter, herbal supplements and health store products) to be taken during the study must be approved by the site principal investigator. Medications that should not be taken at any time during the study include:

- All antidepressants
- Neuroleptics
- Systemic corticosteroids
- Xanthines (i.e., theophilline, theophilline sodium glycinate and aminophylline)
- Medications that interfere with methamphetamine detection in urine samples (e.g. ephedrine and pseudoephedrine)
- Bupropion containing medications (i.e., Wellbutrin[®], Zyban[®])
- The antiretrovirals nelfinavir, and efavirenz
- Tramadol (Ultram, Ultram Extended Release)

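### The protocol's rules on antiretrovirals do not agree: exclusion 12, exclusion 14f and section 12.13 can give one subject different answers, and ritonavir has no clear status

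*Protocol*

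**What the plan says.** Four places in the protocol bear on antiretrovirals.

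- **Section 4.2.5, Drug Interactions.** In vitro work is said to suggest that "nelfinavir, ritonavir, and efavirenz inhibit the hydroxylation of bupropion" (several antidepressants are named in the same sentence). The next sentence says that no clinical study has evaluated this.
- **Section 9.2, exclusion 14.** A participant must not "Be using bupropion or any medication that could interact adversely with bupropion" within a stated interval before dosing. Item f of the examples reads "Antiretrovirals including nelfinavir, and efavirenz".
- **Section 9.2, exclusion 12.** A participant must not "Be undergoing HIV treatment with antiviral and/or non-antiviral therapy since these drugs may increase the bupropion levels". The same item then gives HIV medications that may be "used: Norvir, Reyataz, Truvada, Videx, Viread, Androgel and Trizovir", and closes with a note: "Any HIV medication not on this list should be approved by the medical monitor".
- **Section 12.13.** The medications that should not be taken during the study include "The antiretrovirals nelfinavir, and efavirenz". The section opens by requiring the site principal investigator's approval for any medication taken on study.

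**The concern.** Section 4.2.5 puts three antiretrovirals on the same footing, and the two working lists repeat two of them without explaining why the third is left out. Separately, exclusion 12 bars HIV treatment and also permits some of it, while 14f is worded to reach antiretrovirals as a group.

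What is at stake is consistent enrolment and consistent handling of a medication that the protocol itself treats as a safety matter: its stated reason for exclusion 12 is that HIV drugs may raise bupropion levels. With 5 or more sites planned, staff who start from different criteria could reach different decisions on the same kind of subject.

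**Working it through.** No sample size, power or error rate is involved, so the check sets the texts side by side.

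**Count.** Section 4.2.5 names 3 antiretrovirals. Exclusion 14f names 2 of them and section 12.13 names the same 2. The remainder is 3 − 2 = 1, ritonavir, missing by name from both.

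**Are the lists closed?** No. Exclusion 14 is framed around any adversely interacting medication, and 14f uses an inclusive word before its two examples. The lead-in to section 12.13 is also inclusive, although its antiretroviral entry itself names just the two drugs. Absence of a name therefore does not mean that a drug is allowed.

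**Which rule applies to which drug?** Exclusion 14f can be read broadly (antiretrovirals as a class) or narrowly (the two named).

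| Drug | 14f, broad | 14f, narrow | Exclusion 12 | Section 12.13 |
|---|---|---|---|---|
| Nelfinavir, efavirenz | barred | barred | not listed under these names; medical monitor | not to be taken |
| Ritonavir | barred | not named; depends on the general wording of 14 | not listed under this name; cannot be placed from the protocol | not named; site principal investigator |
| An antiretroviral on exclusion 12's list | barred | not named | may be used | site principal investigator, unless it is one of the two named |
| Any other antiretroviral | barred | not named | medical monitor | site principal investigator |

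**Reading the table.**

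1. On the broad reading, 14f bars any antiretroviral that exclusion 12 lists as usable, and any that the medical monitor might approve. The second conflict does not depend on what the listed brands contain.
2. On the narrow reading that collision goes away for unnamed drugs, but ritonavir is left without a stated status although section 4.2.5 names it with the two that are barred.
3. For nelfinavir and efavirenz, exclusion 12 taken alone points to the medical monitor, while 14f and section 12.13 bar them outright.
4. The approver changes with the section: the medical monitor for unlisted HIV drugs in exclusion 12, the site principal investigator for all on-study medications in section 12.13.
5. Section 4.2.5, 14f and 12.13 use generic names for antiretrovirals and exclusion 12 uses brand names. The protocol does not link the two, so a reader cannot place ritonavir on or off the permitted list from the document alone.

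**The case against.** The case on the other side is substantial.

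- **The lists give examples only.** This stands. The general wording of exclusion 14 could be applied to ritonavir, and its absence from 14f or 12.13 is not permission. But the more weight the open wording of 14f is given, the more directly it conflicts with exclusion 12's permitted list.
- **Exclusion 12 is a bar with exceptions.** It can be read that way: listed drugs may be used, others go to the medical monitor. Taken alone it is workable, though no exception clause is written. The difficulty arises when it is read with 14f.
- **All exclusions apply together, so 14f simply prevails.** This is logically possible, but on the broad reading exclusion 12's permission would then have no effect for any antiretroviral, which can hardly be the intention.
- **Review is already in place.** This stands in part. Section 13.6.26 has prior medications reviewed and approved at the site, section 13.6.12 has reported medications checked for interactions, section 12.13 requires approval, and exclusion 12 brings in the medical monitor. These controls make an unnoticed error less likely. They do not tell the reviewers which criterion governs, and they name different approvers.
- **The evidence is in vitro only.** This is correct, and leaving ritonavir out may have been deliberate. The protocol gives no reason, and it describes the evidence in the same terms for all three drugs.

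Three stronger readings are tempting and are not supported:

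- **Raised seizure risk.** A reader might infer this for subjects on ritonavir. Section 4.2.5 makes its dose-dependence remark about concurrent bupropion-containing products and names no antiretroviral in its discussion of seizure risk.
- **Spoiled bupropion-level analyses.** A measured plasma level is the subject's actual exposure, and concomitant medications are recorded, so affected subjects can be identified.
- **Express permission of ritonavir under a brand name.** The protocol does not say what the listed brands contain, so this would rest on an outside source.

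**Conclusion.** The inconsistency is real and limited. Exclusion 12, exclusion 14f and section 12.13 do not give one rule for antiretrovirals. On a broad reading of 14f, a subject could be excluded under it and admitted under exclusion 12. On a narrow reading, one of the three drugs that section 4.2.5 names as inhibitors has no stated status. Existing investigator and medical-monitor review partly mitigates this.

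The number of subjects affected cannot be derived. The notes to section 9.2 allow a positive HIV antibody titre and exclude AIDS, but seropositivity is not the same as being on treatment, so this gives no estimate. The planned 200 subjects and the primary comparison of abstinence in Weeks 11 and 12 are unaffected.

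The collision with the permitted list assumes that at least one brand on it is an antiretroviral. The conflict with the medical-monitor route does not need that assumption.

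**What to change.** The sponsor's medical staff should reconcile section 4.2.5 (Drug Interactions), section 9.2 (criteria 12 and 14f) and section 12.13:

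- Use one naming convention throughout, or give generic and brand names together.
- Give each antiretroviral named as interacting one status, the same at screening and on study, or state why the two differ.
- State whether 14f covers antiretrovirals as a class or only named drugs, and how it relates to exclusion 12's permitted list.
- Name one approver for HIV medications, at screening and on study.

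No position is taken on which status any drug should have.

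The cost is protocol wording and a matching update to the eligibility checklist. No visits, procedures or subjects are added.
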